#### **4.1.3. Dose Modification Guidelines**

Dose modifications may only be considered in cycles after Cycle 1 during Part 1 (Dose Escalation). Dose modifications may be considered during any cycle in Part 2A and 2B (Dose Expansion and Dose Optimization). In the circumstance that a subject enrolled in Part 1 has experienced an event that qualifies as a DLT the subject must be discontinued from the study and followed for resolution of AEs. Following the DLT assessment period, doses may be held or modified for specific AEs and/or laboratory abnormalities in Cycles 2+ for subjects participating in the dose escalation part and in all cycles for subjects in the dose expansion part.

##### **4.1.3.1. Dose Reductions and Interruptions**

Subjects who experience an AE at any time during the study are permitted to undergo approved dose interruptions; subjects must continue to fulfill the Dosing Criteria in [Protocol Section 6.1.2](#) and [Protocol Section 6.1.3](#) prior to each dose.

Subjects are not permitted to undergo dose reductions during the DLT assessment period other than temporary study discontinuation of study medication as provided in Individual Stopping Rules.

Additional dose modification instructions are found in the [Protocol Section 6.1.4](#).

## **4.2. Method of Assigning Subjects to Treatment Groups**

### **4.2.1. Subject Assignment in Part 1 Dose Escalation**

Subjects who successfully complete the inclusion/exclusion screening phase and provide informed consent will be enrolled into the currently available dose cohort within 28 days of completing the screening. Inclusion and exclusion criteria are described in the [Protocol Section 4.2](#).

### **4.2.2. Subject Assignment in Part 2A and 2B Tumor-Specific Dose Expansion and Dose Optimization**

Subjects who successfully complete the inclusion/exclusion screening, including the additional Part 2A and 2B (Tumor-Specific Dose Expansion and Dose Optimization) inclusion screening criteria, and provide informed consent will be enrolled into the respective tumor-specific cohort at the MTD/MAD or SRC recommended dose. Additional screening criteria are described in the [Protocol Section 4.2.2](#).

## **4.3. Blinding and Unblinding**

This is a FIH, open-label, multicenter, Phase I study in which all subjects receive the investigational product, KZR-261, without randomization. As such, the study is unblinded.

## **5. SAMPLE SIZE AND POWER CONSIDERATIONS**

The sample size for Part 1 will be approximately 70 subjects, but the actual sample size will depend on the number of dose levels of KZR-261, number of subjects per dose level, and the number of subjects treated at the MTD or the MAD(s) of KZR-261.

Dose escalation will continue accruing until one of the three stopping conditions below is triggered:

- The maximum sample size has been achieved,
- MTD/MAD has been identified with sufficient accuracy: data from 6 to approximately 12 subjects have been accumulated at a dose that is deemed to be the MTD/MAD, or
- All doses explored appear to be overly toxic and the MTD cannot be determined.

Due to binomial data variability in small samples, DLTs may be observed in a first cohort(s) by chance even when the true probability (DLT) is fairly low. This could result in the estimated posterior DLT rate exceeding the targeted 30% very early in the trial, triggering an early stop when very few subjects (2-4) have been treated. To prevent stopping the trial prematurely in such cases, a step-down option with a lower dose of 0.9 mg/m^2 is added to the dose grid. This dose

will be explored only if a high DLT rate occurs in the first cohort assigned to 1.8 mg/m^2, ie, it will not be used as a starting dose.

Upon identification of the MTD/MAD at the conclusion of Part 1, the study will continue with up to 4 tumor-specific expansion cohorts and 1 All-Tumors cohort in Part 2A. As previously noted, the tumor-specific cohorts (n = 15 at interim) may be increased up to 35 subjects per cohort to more precisely estimate the anti-tumor activity of KZR-261, if there is a sufficient efficacy signal at the interim analyses ([Protocol Section 10.6](#)) and if the tumor type is not selected for investigation in Part 2B (dose optimization). The All-Tumors cohort may enroll up to 35 biopsy-evaluable subjects.

Go/No-Go futility analysis for each tumor-specific cohort in Part 2A will be based on CBR as the primary outcome measurement (as defined in [Protocol Section 10.5.5](#)) after Stage 1 enrollment of 15 subjects. Each of the expansion cohorts is based on the following assumptions:

- At the interim analysis, if there is 1 or no subject with clinical benefit (ie, CBR rate <7%), further enrollment into the cohort will be stopped for futility. If futility is rejected at the interim analysis (ie, 2 or more of 15 subjects with clinical benefit), the final analysis will be based on a total 35. Note: Outcomes (ie, presence or absence of clinical benefit) for subjects enrolled in Part 1 with the same tumor type and who received the same dose of KZR-261 as evaluated in the corresponding Part 2A, tumor-specific cohort may be included among the initial 15 subjects at the interim analysis, as described above.

The operating characteristics of this design are presented in [Table 3](#). If the true CBR is less than 5%, there is an 83% probability to reach the futility criterion at interim. On the other hand, if the true CBR is 20% or higher, the probability to stop for futility is 17%.

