3.2.2. Intra-subject Dose Escalation

Intra-subject dose escalation will be permitted after consultation with the Medical Monitor and in the following circumstance only:

- Subject must have completed at least two 28-day cycles of treatment (Cycles 1 and 2).
- Subject who experienced an AE* \leq Grade 3 with resolution to Grade 1 or baseline in the setting of a documented tumor response or stable disease over 2 consecutive assessment timepoints. For subjects who experienced a Grade 3 AE, the Investigator and Medical Monitor should come to an unequivocal consensus that the potential benefit of an increase in dose is likely to outweigh the risks.
- Subject must not have experienced a DLT.

- Subject must not have experienced a dose reduction for purposes of managing AEs and/or laboratory abnormalities.
- The higher dose cohort to which the subject would be escalated has been deemed by the SRC to be safe and adequately tolerated.

** AEs must be assessed as unrelated to study treatment, such as intercurrent illness or concomitant medication. AEs that are assessed as related to study treatment would disqualify a patient from dose escalation.*

3.2.3. Definition of Dose-Limiting Toxicity for Part 1

A DLT is defined as an AE or abnormal laboratory value that occurs during the first 28 days of treatment (Cycle 1) and meets the criteria listed below, unless it is assessed to be related to the disease under study, intercurrent illness, or concomitant medications.

Toxicities will be assessed by the Investigator using the NCI CTCAE v5.0. AEs that are not listed in the NCI CTCAE are to be assessed using the criteria in [Section 9.1.2](#). The attribution of an AE is to be assessed by the Investigator using the criteria in [Section 9.1.3](#).

Subjects who experience a DLT in Part 1, Cycle 1 must be withdrawn from study treatment and will not be replaced. Subjects enrolled in Part 1 who discontinue from study treatment for reasons other than a DLT prior to completion of the DLT assessment period ([Section 3.2.3](#)) may be replaced. AEs that meet the definition of a DLT that are reported after Cycle 1 will be taken into consideration for dose escalation decisions and to help determine the dose for further investigation in Part 2.

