All subjects considered for enrollment into Part 2 of the study must meet the following criteria in addition to the criteria listed in [Section 4.2.1](#):

18. Subjects who agree to submit fresh or archived tumor tissue must do so during the Screening period tissue.
19. For subjects who have **cutaneous melanoma**:
 - a. Must have histologic or cytologic evidence of disease that is locally advanced or metastatic (American Joint Committee on Cancer [AJCC] Stage 3 or 4).
 - b. Must have relapsed or be refractory to treatment with currently approved therapies, including an immune checkpoint inhibitor(s), or unable to tolerate approved therapy(ies).
 - c. For subjects with a RAF V600 mutation, the subject may have received therapy with a small molecule RAF V600 inhibitor with or without a small molecule MEK inhibitor.
20. For subjects who have **uveal melanoma**:
 - a. Must have histologic or cytologic evidence of locally advanced unresectable or metastatic uveal melanoma.
 - b. Disease must be treatment naive or have progressed (radiologically or clinically) on most recent therapy.
21. For subjects who have malignant mesothelioma of the peritoneum or pleura:
 - a. Must have histologic or cytologic evidence of malignant mesothelioma that is either metastatic or locally advanced and not amenable to surgical resection or treatment with localized therapies.
 - b. Must have been previously treated with an acceptable platinum-based regimen (eg, cisplatin or carboplatin combined with pemetrexed).

- c. The subject may have received Tumor Treating Fields (TTFields).
- d. Has previously received treatment with an approved immunotherapy unless the subject is not a candidate for immunotherapy.

22. For subjects who have **mCRPC**:

- a. Must have histologically or cytologically documented, locally advanced unresectable or metastatic adenocarcinoma of the prostate.
- b. Must have disease progression despite castration by orchiectomy or ongoing luteinizing hormone-releasing hormone (LHRH) analogue.
- c. Must have disease that progressed on or after treatment with androgen inhibitors.
- d. Must have prior treatment with a taxane or not be a candidate for treatment with a taxane.
- e. Must have prior treatment with an inhibitor of poly ADP-ribose polymerase (PARP) if the subject has a deleterious germline or somatic BRCA 1/2 mutation or another homologous recombination repair gene mutation.

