- f. Must have progressive disease as defined by PCWG3 criteria ([Scher et al., 2016](#)).
Note: Patients with biochemical progression (ie, rising PSA levels) only are not eligible.
- g. Must have measurable or evaluable disease. Eligible subjects must have at least one measurable lesion per RECIST v1.1 and/or evidence of relapse/progression in bone per PCWG3.

23. For subjects who have **mCRC**:

- a. Must have histologic or cytologic evidence of CRC that is locally advanced and unresectable or metastatic.
- b. Must have received or demonstrated intolerance to, appropriate therapy consisting of a fluoropyrimidine-based regimen with oxaliplatin and/or irinotecan with or without a therapeutic targeting VEGF, and with a monoclonal antibody (mAb) targeting EGFR, if their tumor lacks a KRAS mutation.
- c. If the subject has a tumor with a RAF V600 mutation, the subject must have received, or demonstrated intolerance to, appropriate therapy targeting RAF V600 with or without a small molecule MEK inhibitor plus a mAb targeting EGFR.
- d. If the subject has a tumor that is microsatellite instability high (MSI-H), the subject must have received or demonstrated intolerance to therapy targeting PD-1.
- e. Must have received no more than 4 prior lines of therapy for mCRC (adjuvant therapy does not count as a line of treatment).

24. For subjects who have relapsed or refractory solid tumors in the All-Tumors cohort (Part 2A), excluding primary CNS malignancies.

- a. Must be able to submit fresh tumor tissue during the Screening period. Exceptions to this requirement may be considered after discussion with the Medical Monitor.
- b. [Appendix C](#) includes a list of prioritized tumor types.

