10.6. Interim Analyses

The Go/No-Go futility analysis for each tumor-specific cohort in Part 2A will be based on CBR as the primary outcome measurement (as defined in [Section 10.5.5](#)) after Stage 1 enrollment of 15 subjects. Each of the expansion cohorts is based on the following assumptions:

- Each expansion cohort has a maximum sample size of 35 with one interim futility analysis at 15 subjects. At the interim analysis, if there is 1 or no subject with CBR (ie, CBR rate <7%), further enrollment into the cohort will be stopped for futility. If futility is rejected at the interim analysis (ie, 2 or more of 15 subjects with clinical benefit), the final analysis will be based on a total 35 subjects (ie, 20 additional subjects evaluable for CBR). Note: Outcomes (ie, presence or absence of clinical benefit) for subjects enrolled in Part 1 with the same tumor type and who received the same dose of KZR-261 as evaluated in the corresponding Part 2A, tumor-specific cohort may be included among the initial 15 subjects at the interim analysis, as described above.

The operating characteristics of this design are presented in [Table 13](#). If the true CBR is less than 5%, there is a reasonable chance to reach the futility criterion at interim. On the other hand, if the true CBR is 20% or higher, the probability to stop for futility is moderately low (<20%).

Table 13: Operating Characteristics of Dose Expansion Phase (Part 2A)

True CBR	Interim Analysis (N=15)		Final Analysis (N=35)		
	Pr(Futility*)	Pr(obs. CBR ≥15% 6 or more subjects with CBR)	Pr(obs. CBR ≥20% 7 or more subjects with CBR)	Pr(obs. CBR ≥25% 9 or more subjects with CBR)	Pr(obs. CBR ≥25% 9 or more subjects with CBR)
5%	83%	<1%	<1%	<1%	<1%
10%	55%	11%	5%	<1%	<1%
15%	32%	39%	25%	7%	7%
20%	17%	67%	54%	25%	25%
25%	8%	86%	78%	52%	52%
30%	4%	95%	92%	76%	76%
35%	1%	98%	97%	91%	91%

CBR=clinical benefit rate; obs.=observed; Pr=probability

* 1 or fewer subjects with CBR among the first 15 subjects.

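### As worded, the Stage 1 futility count may include Part 1 subjects who were escalated into the Part 2A dose, and who are therefore selected for not having progressed

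*SAP*

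**What the plan says.** **The rule.** SAP section 5 states that "if there is 1 or no subject with clinical benefit (ie, CBR rate <7%), further enrollment into the cohort will be stopped for futility". With 2 or more of 15, the cohort may go on to 35. Protocol 10.6 has the same rule.

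**The reuse note.** Outcomes of "subjects enrolled in Part 1 with the same tumor type and who received the same dose of KZR-261" as the Part 2A "tumor-specific cohort may be included among the initial 15 subjects at the interim analysis". Protocol 10.6 says the same of a Part 1 subject "who received the same dose of KZR-261 as evaluated in the corresponding Part 2A, tumor-specific cohort may be included among the initial 15 subjects", and so does the synopsis. There are two conditions, tumor type and dose received, and inclusion is optional.

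**Intra-subject escalation.** Protocol 3.2.2 lets a Part 1 subject move to a higher dose that the Safety Review Committee (SRC) has cleared, once two 28-day cycles are complete. Its bullet on subjects who have had an adverse event (AE) places this "in the setting of a documented tumor response or stable disease over 2 consecutive assessment timepoints".

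**Clinical benefit.** SAP 13.2.5 counts a best response of CR, PR, or SD over at least two assessments. SAP 13.2 takes best overall response over the whole treatment period, from its start. Progression ends treatment (Protocol 3.1 and 8.1.2), and scans fall after every second cycle (Protocol 7.2.10).

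**Entry criteria.** The tumor-specific criteria of Protocol 4.2.2 are for Part 2: "All subjects considered for enrollment into Part 2 of the study must meet the following criteria". One example, for colorectal carcinoma, is "Must have received no more than 4 prior lines of therapy for mCRC". Part 1 has no such limit.

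**The concern.** A subject who started at a lower dose and was escalated into the dose later chosen for Part 2A has, on the plain words, received that dose. To get there the subject had to finish two cycles, and so pass the first scheduled scan without progression. Under the AE bullet the subject may already satisfy the clinical benefit definition. Because best response runs from the start of treatment, benefit reached at the lower dose would then be credited to the Part 2A dose. This is selection on the outcome that the futility rule counts.

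The overlap is plausible. Protocol 3.2.1.1 allows backfilling at lower, already cleared dose levels and prefers the four Part 2A tumor types for it.

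The 2-of-15 rule is the prespecified efficacy check before up to 20 more subjects are treated in a cohort. Its stopping probabilities hold only if all 15 share one benefit rate. The final analysis is described as the 15 plus 20 more, so on that arithmetic a reused subject would also enter the final estimate.

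A second, smaller gap is that a shared tumor type does not mean a Part 1 subject would have qualified for the Part 2A cohort.

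**Working it through.** **Inputs.** From SAP section 5 and Protocol 10.6: n = 15, stop at 0 or 1 with benefit. From SAP Table 3 (Protocol Table 13): true CBR p. Assumptions, because the documents give neither: k, the number of escalated Part 1 subjects among the 15, and q, their probability of counting as clinical benefit. SAP section 18 words the threshold differently; the rule used here is the one behind Table 3.

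**Step 1: reproduce the printed figures.** Pr(stop) = (1−p)^15 + 15p(1−p)^14. For p = 5, 10, 15, 20, 25, 30 and 35% this gives 82.9, 54.9, 31.9, 16.7, 8.0, 3.5 and 1.4%. The table prints 83, 55, 32, 17, 8, 4 and 1%. The arithmetic is correct and rests on one common CBR.

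**Step 2: one escalated subject (k = 1).** Pr(stop) = q(1−p)^14 + (1−q)·Pr(X ≤ 1 of 14).

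At p = 5%, 0.95^14 = 0.488 and Pr(X ≤ 1 of 14) = 0.847, so:

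- q = 0.3: 0.3×0.488 + 0.7×0.847 = 0.739
- q = 0.5: 0.5×0.488 + 0.5×0.847 = 0.667
- q = 1: 0.488

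**Step 3: two escalated subjects (k = 2).** Pr(stop) = (1−q)²·Pr(X ≤ 1 of 13) + 2q(1−q)(1−p)^13.

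At p = 5%, 0.95^13 = 0.513 and Pr(X ≤ 1 of 13) = 0.865, so:

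- q = 0.3: 0.49×0.865 + 0.42×0.513 = 0.639
- q = 0.5: 0.25×0.865 + 0.50×0.513 = 0.473
- q = 1: 0, because two benefits are already in hand

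**Step 4: summary of Pr(stop).**

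| True CBR | Printed | k | q = 0.3 | q = 0.5 | q = 1 |
|---|---|---|---|---|---|
| 5% | 83% | 1 | 74% | 67% | 49% |
| 5% | 83% | 2 | 64% | 47% | 0% |
| 10% | 55% | 1 | 48% | 41% | 23% |
| 10% | 55% | 2 | 41% | 28% | 0% |

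**Step 5: which q applies.** Values near 1 fit a subject escalated under the AE bullet, whose response or repeated stable disease is close to the CBR definition. A subject with no AE who is escalated straight after Cycle 2 has had one scheduled scan. Without a response at that scan, the second stable-disease assessment is still to come and would fall at the higher dose. For that subject q is raised above p by the selection, but by an unknown amount.

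**Step 6: the eligibility gap.** Suppose ineligible Part 1 subjects have CBR 5% and the others 20%. Pr(stop) then rises from 17% to 19% with one and 22% with two. With five it is 31%: Bin(5, 0.05) plus Bin(10, 0.20) gives Pr(≤ 1) = 0.313. If such subjects had a higher CBR than the cohort, the change would go the other way.

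**The case against.** The strongest reply is that the note means the assigned dose. Part 1 data are summarised by dose level, disposition listings carry the assigned dose, and Part 2A evaluates one dose from Cycle 1. That may well be the intent, but neither document says so for this count; if it is the intent, the fix only writes it down.

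Other parts of the reply stand and limit the point:

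- **Escalated subjects need not be counted.** A reader might infer that they will be. The text is permissive, so they can count.
- **Benefit is not guaranteed.** The response or stable-disease condition sits in the bullet on subjects with an AE. The 49% and 0% figures are the upper end of the effect.
- **Such subjects may be few.** Each must match the tumor type, have no DLT, no dose reduction and no treatment-related AE, and still be on treatment when the relevant dose is cleared. No count per cohort can be derived.
- **Two benefits in hand do not force expansion.** A reader might infer this from the 0%. SAP 4.1.2 leaves the decision to the SRC, and Protocol 10.1.2 says that cohorts may be increased, and only if the tumor type has not been selected for Part 2B.
- **The 31% against 17% comparison is an extreme case.** It needs five ineligible subjects of one tumor type, when 6 to about 12 subjects of all types are planned at the putative MTD/MAD (the SRC may add more). The direction is not fixed either.

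**Conclusion.** The point holds as a gap in wording that a single clause closes. The two stated conditions do not keep out subjects escalated into the Part 2A dose, and no other section of either document does so. Each such subject would weaken the stop in a cohort with little activity. At a true CBR of 5%, one takes the stopping probability from 83% to between 74% and 49%, and two take it to between 64% and 0%, for q from 0.3 to 1. These ranges rest on assumed k and q. Table 3 itself is correct for 15 subjects with one common rate.

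The documents do not support reading this as a futility rule that is already disabled, or as a known net bias. Inclusion is optional, the number of affected subjects is unknown, and passing the rule is not a commitment to expand. Optional inclusion is little protection in an open-label trial, however, and making inclusion mandatory under the present wording would not cure the selection. The eligibility gap is secondary.

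**What to change.** In SAP section 5, Protocol 10.6 and the synopsis, replace the condition on dose received with: was assigned to, and started Cycle 1 Day 1 at, the dose evaluated in the corresponding Part 2A cohort. State that subjects escalated into that dose are not counted. Secondarily, add that a Part 1 subject is reused only if the recorded data show that the cohort's tumor-specific criteria in Protocol 4.2.2 were met at entry.

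With these limits the reused subjects are no longer selected on the outcome, and the common-rate assumption behind Table 3 is reasonable again. No dose, escalation rule or planned sample size changes.

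Costs: a protocol amendment with IRB/IEC approval, and fewer reusable Part 1 subjects, so that more of the 15 planned places are filled by Part 2A subjects. The eligibility check also has a practical limit. Some criteria for prostate and colorectal cancer depend on mutation or microsatellite status, and Protocol 7.2.1 has the tumor mutational profile recorded only if known. Subjects without the needed data would not be reused.

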**Table 3: Operating Characteristics of Dose Expansion Phase (Part 2A)**

True CBR	Interim Analysis (N=15)		Final Analysis (N=35)		
	Pr(Futility*)	Pr(obs. CBR ≥15% 6 or more subjects with CBR)	Pr(obs. CBR ≥20% 7 or more subjects with CBR)	Pr(obs. CBR ≥25% 9 or more subjects with CBR)	
5%	83%	<1%	<1%	<1%	
10%	55%	11%	5%	<1%	
15%	32%	39%	25%	7%	
20%	17%	67%	54%	25%	
25%	8%	86%	78%	52%	
30%	4%	95%	92%	76%	
35%	1%	98%	97%	91%	

CBR=clinical benefit rate; obs.=observed; Pr=probability

\* 1 or fewer subjects with CBR among the first 15 subjects.

In Part 2B (Dose Optimization), up to 120 subjects may be enrolled into up to 4 tumor-specific cohorts (30 per each tumor-specific cohort [15 per dose level]) based on the totality of data after data from Parts 1 and 2A has been assessed. The sample size for Part 2B is based on clinical considerations.

## **6. ANALYSIS POPULATIONS**

### **6.1. Safety Population**

The Safety Population consists of all subjects who receive at least 1 dose of study treatment (KZR-261) and will be used for the safety analyses.

